3.4.4.3 Concomitant medication

Concomitant medication and non-drug therapies will be listed.

For the whole analysis population incidences of concomitant medications by ATC Level 3 and Preferred Name (using the WHO Drug Global Dictionary release September 1, 2019) will be generated.

3.4.5 Pharmacokinetic and pharmacodynamic analyses

Not applicable.

3.5 Data handling conventions

All data management procedures will be detailed in separate, specifically identified files that collectively will be referenced as the Data Management Plan (DMP).

The study will utilize eCRFs, which will include validated 21CFR Part 11 compliant electronic data capture (EDC) software, to collect data. All requested information must be entered on the eCRFs in the areas provided in a timely manner. When changes or corrections are made in the eCRF, the EDC system will maintain a complete audit trail of the person making the changes, the date and time of the change, and the reason for the change.

Adverse event, medical history and procedure terms will be coded using the MedDRA dictionary (Version 22.1) according to the ICH MedDRA Term Selection: Points to Consider release 4.18. All MedDRA coded terms will be provided with all 5 levels, from System Organ Class to Lowest level term, including associated codes.

Prior and concomitant medication will be coded using the WHO Drug Global Dictionary release September 1, 2019. Route, indication and drug manufacturing country will be taken into account when determining the proper coding assignment. Product Name, Medical Product ID, Preferred Name, Drug Code and ATC Levels 1-4 with associated codes will be provided.

The data will be checked and the database structure validated. Once all queries are resolved satisfactorily, the database will be locked. The locked SAS Database will be used to generate the subject listings, tabulations, and analyses.

Page 19 of 21

All data associated with the clinical database, including eCRF data, all external data such as medical coding, third party data will be protected from any changes and afterwards approved by 'Clinical Database Lock Form'.

3.5.1 Missing data

Missing data will not be estimated and/or imputed in any way.

A description of missing data will be provided in the clinical investigation report.

In case a subject prematurely discontinues the clinical investigation (except withdrawal of consent), following assessments should be done at minimum: AE assessment and concomitant medication. Attempts should be made to perform an early termination visit, which should consist of the assessments planned for the Week 104 visit (see section 2.3): AE assessment and concomitant medication, photo documentation, NLF-SRS, GAIS, Face-Q Satisfaction-withoutcome Scale, aesthetic effect by the investigator.

In case of premature discontinuation from the clinical investigation, safety assessments performed at the time point of withdrawal will be reported together with the end of trial visit.

Performance assessments at withdrawal will be assigned for analysis to the closest missing visit before withdrawal, if the subject's withdrawn is between the scheduled visits.

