#### 7.1 Sample size

Up to approx. 100 + 10 subjects with moderate to severe nasolabial folds will be randomized with a 1:1 allocation to the manufacturing sites C1 and HQ, in order to obtain the 24-week performance and safety data from approximately 50 of them in each manufacturing site. This sample size is considered appropriate for the clinical investigation and sufficient to provide robust estimations on performance and safety parameters in the study population. A sample size of approximately 50 allows a meaningful range estimation, the confidence interval, for the true proportion of success (reduction in NLF-SRS grades of  $\geq$ 1) at week 24. With a sample size of 50, a confidence level of (1-  $\alpha$ ) with  $\alpha$ =0.05 and an estimated proportion of 0.9 a two-sided 95% confidence interval for the true proportion using the large sample normal approximation is given through [0.817; 0.983]. Thus, in compliance with the study design, the true proportion is expected in the range of the confidence interval with an error probability of 5%.

A 'responder' is defined having at least  $\geq$  1 grade improvement as evaluated with the 5 point-validated NLF-SRS at week 24 relative to Baseline (Day 0) score on both sites. Individual NLF-SRS grades per visit will be assessed separately for the right and left NLF. A Response rate of 90% at week 24 is estimated.

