3.3 Analysis sets

All safety analyses will be based on the Safety analysis set, defined as all subjects who received the IMD.

The Intent-to-Treat (ITT) population is defined as all subjects who received the IMD and have at least one post-treatment assessment. The ITT population will be the primary analysis population for analyses of performance of the investigational device and of aesthetic effects in interim and in final analysis.

Page 15 of 21

The assignment of subjects to the safety analysis set and to the ITT population will be done prior to the interim analysis after Week 24.

A Per-Protocol (PP) population is defined to provide sensitivity analyses in the final analysis. The PP population comprises all subjects in the ITT population, who completed the Week 24 assessment without any major CIP deviations (i.e. CIP deviations that interfere with the performance evaluation or the aesthetic effect evaluation).

Subjects will be excluded from the PP population,

- who violated any inclusion/exclusion criteria during the course of the study;
- who's primary performance outcome measure, the ≥1-point improvement over Baseline on the NLF-SRS based on investigator's live assessment at Week 24 is missing, except it is a missing assessment for treatment related reason, e.g. discontinuation of assessments due to adverse events at least possibly related to IMD or due to lack of efficacy;
- who received any medication or procedure interfering with the performance or aesthetic effect evaluation at Week 24.

Prior to the final statistical analysis, other additional criteria may be added to the list to accommodate for unforeseen events that occurred during the conduct of the trial that result in noteworthy study protocol violations.

The assignment of subjects to the PP population will be finalized within a data review meeting for the final analysis.

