3.4 Statistical methods

The final statistical analysis will be done after completion of the investigation by all subjects. The interim analysis will be done after all subjects have completed the Week 24 study procedures.

In general, collected data will be listed and descriptive statistics will be performed, with all repeating measurements being tabulated by visit.

For qualitative and discrete variables, the total number of observations, frequency and percentages of categories / scores will be calculated.

Quantitative and continuous variables will be described by declaring descriptive summary statistics (number of observations, the mean value, standard deviation, minimum, first quartile, median, third quartile, and maximum).

Two-sided 95% confidence intervals will be calculated assuming normal distribution, if not stated otherwise.

The primary and secondary performance analysis and the safety analysis will be done for each manufacturing site, C1 and HQ, separately and for the whole analysis population. The exploratory performance analysis will be done for the whole analysis population, ITT and PP respectively, only.

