3.4.3.2 Statistical analyses

The performance analyses will be done in the Intent-to-treat population. Additionally certain analyses will be presented for the per-protocol population also to provide sensitivity analyses in the final analysis.

Individual NLF-SRS grades per visit will be calculated as the mean of grades assigned to the left and the right NLF, respectively, for descriptive summaries.

The improvement over Baseline in the NLF-SRS grade assessed by the investigator will be computed for each subject by subtracting the NLF-SRS grade obtained at each post-baseline time point from ipsilateral NLF-SRS grade obtained at Baseline. The individual improvement per visit will be calculated as the mean of both improvements in the left and the right NLF, respectively, for descriptive summaries.

The response rate will be calculated as the proportion of subjects with NLF-SRS improvement (i.e, reduction in NLF severity grade) of a \geq 1 point in both NLFs. The proportion of subjects with NLF-SRS improvement of \geq 2 points in both NLFs will be determined accordingly.

Two-sided 95% confidence intervals for the percentages of responders at various time points will be given for the proportions of the NLF-SRS improvements of ≥ 1 or ≥ 2 points, respectively using the large sample normal approximation. Also, two-sided 95% confidence intervals for the mean of individual NLF-SRS improvement at various time points will be calculated assuming normal distribution.

Summaries will be provided for the whole analysis population, as well as within each manufacturing site, C1 and HQ, separately.

Primary performance outcome measures

For the primary performance outcome measure, the percentage of responders with a \geq 1-point improvement over Baseline on the NLF-SRS based on investigator's live assessment at Week 24, the following will be given by manufacturing site and for the whole analysis population:

• percentage of responders with a ≥1-point improvement over Baseline on the 5-point NLF SRS, based on investigator's live assessment at Week 24 after initial treatment,

Secondary performance outcome measures

For secondary performance outcome measures the following will be given by manufacturing site and for the whole analysis population:

 percentage of responders with a ≥1-point improvement over Baseline on the 5-point NLF SRS, based on investigator's live assessment at Week 4, 36, 52 and optional at Week 65, 78 and 104 after initial treatment,

Page 17 of 21

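### The Week 24 responder rate has no stated denominator; on the likely observed-case reading, failures who leave early are omitted, and the per-protocol exemption gives them no outcome

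*SAP*

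**What the plan says.** SAP 3.4.3.2 defines the endpoint: "The response rate will be calculated as the proportion of subjects with NLF-SRS improvement" of at least one point in both folds. The analysis is in the ITT population, which SAP 3.3 limits to treated subjects with some assessment after treatment. The denominator at a given visit is not written.

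Three other places point to observed cases:
- Protocol 7.1 and SAP 2.2 randomise about 110 subjects "in order to obtain the 24-week performance and safety data from approximately 50 of them in each manufacturing site", and size the confidence interval on 50.
- SAP 3.4 sets the general rule: "For qualitative and discrete variables, the total number of observations, frequency and percentages of categories" are calculated.
- Protocol 7.3 and SAP 3.5.1 both state: "Missing data will not be estimated and/or imputed in any way".

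SAP 3.5.1 moves a performance grade taken at withdrawal back to the nearest earlier visit that is missing. SAP 3.5.2 lists, without analysing, anything that cannot be assigned to a planned visit.

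For the per-protocol (PP) set, SAP 3.3 admits ITT subjects "who completed the Week 24 assessment without any major CIP deviations". Protocol 7.2 has the same condition. SAP 3.3 then excludes subjects who lack the Week 24 primary outcome, with this exemption: "except it is a missing assessment for treatment related reason, e.g. discontinuation of assessments due to adverse events at least possibly related to IMD". Its second example is lack of efficacy. It gives the exempted subjects no outcome. SAP 1.3 reports no change from the protocol's statistical section.

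On timing, SAP 3.3 says: "A Per-Protocol (PP) population is defined to provide sensitivity analyses in the final analysis". SAP 4 runs the Week 24 interim performance analysis on ITT only.

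**The concern.** A subject who leaves because the filler did not work, or because of an adverse event attributed to it, is a treatment failure. If the rate is taken over subjects with a Week 24 grade, that failure disappears from both numerator and denominator and the rate rises. Even an observed failing grade can be lost. A subject seen at Week 4 and graded as unimproved on withdrawal at, say, Week 20 has no earlier missing visit to receive the grade, so it is only listed.

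The PP analysis is the planned sensitivity check, and its exemption shows that the authors had these subjects in mind. Without an assigned outcome, however, an exempted subject contributes nothing to the Week 24 PP rate. The interim report has no planned sensitivity analysis at all. In an estimation study the rate and its interval are the result, and Protocol 3.3 says that the data should support approval.

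**Working it through.** **Inputs.** Assumed response 0.90, n = 50 per manufacturing site, two-sided 95% normal-approximation interval (Protocol 7.1, SAP 2.2). About 110 subjects randomised 1:1, so about 55 per site, with about 10 dropouts (Protocol 6.3.1) and no replacement (Protocol 6.1.7). The documents do not say how many dropouts are failures, so that number is varied. All 110 are assumed to be in ITT.

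**Formula.** p ± 1.96 × sqrt(p(1 − p)/n).

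**The plan's figure.** 0.90 ± 1.96 × sqrt(0.9 × 0.1/50) = 0.90 ± 0.083 = [0.817; 0.983]. This reproduces the stated interval. Pooled: 90/100 gives 0.90 ± 0.059 = [0.841; 0.959].

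**Per site.** 45 responders among 50 observed, with f of the 5 dropouts counted as non-responders and the others left out: 45/(50 + f).

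| f | Rate | 95% interval |
|---|---|---|
| 0 | 45/50 = 90.0% | 81.7 to 98.3 |
| 1 | 45/51 = 88.2% | 79.4 to 97.1 |
| 2 | 45/52 = 86.5% | 77.3 to 95.8 |
| 5 (bound) | 45/55 = 81.8% | 71.6 to 92.0 |

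**Pooled.** 90/(100 + f), with f out of 10.

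| f | Rate | 95% interval |
|---|---|---|
| 0 | 90/100 = 90.0% | 84.1 to 95.9 |
| 2 | 90/102 = 88.2% | 82.0 to 94.5 |
| 4 | 90/104 = 86.5% | 80.0 to 93.1 |
| 10 (bound) | 90/110 = 81.8% | 74.6 to 89.0 |

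Other bound, with every dropout a responder: 100/110 = 90.9% [85.5; 96.3].

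**Effect of the PP exemption.** Take one exempted failure in a site and no other PP exclusions. As written, the subject is in the set but has no Week 24 value, so the rate is 45/50 = 90.0%, the same as if the subject had been excluded. With a non-response assigned it is 45/51 = 88.2%. The exemption therefore leaves the Week 24 PP rate unchanged.

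**The case against.** **The denominator is open.** A reader might infer that the plan definitely drops failures from the primary rate. The documents do not establish that. Dividing responders by all ITT subjects would also impute no grade, and would count these failures as non-responders. Observed cases is the likelier reading; what can be shown is that the rule is missing.

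**Such exits may be few.** Treatment is one application with an optional touch-up, lack of efficacy is not among the withdrawal reasons in Protocol 6.3.6, and the disruption that the documents expect is COVID-related (Protocol 4.6 and 10). This stands as a limit on size. SAP 3.3 nevertheless provides for these exits, so they need an outcome.

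**The interim is not blind to missing data.** The number of observations, a listing of dropouts with reasons (SAP 3.4.2) and a description of missing data in the report (SAP 3.5.1) are planned. A reader could work out a worst case from them, but no such analysis is planned.

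**An exception after a general rule is ordinary drafting.** That is fair, and the exemption can still matter for PP results at other visits such as Week 4. It does not supply a Week 24 outcome, and it does not remove the departure from Protocol 7.2.

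**Two stronger readings are not supported.**
- One might infer that grades after a non-protocol correction wrongly inflate the ITT rate. Such a grade can enter ITT, because withdrawal is optional under Protocol 6.3.6. But Protocol 7.2 puts all collected data in the ITT data set, so how to treat these grades is an estimand choice. Correction is also prohibited (Protocol 6.4.12), deviations are reviewed before lock (Protocol 10), and the PP set removes anyone "who received any medication or procedure interfering with the performance or aesthetic effect evaluation at Week 24".
- One might infer that SAP 3.5.1 to 3.5.3 contradict each other on withdrawal grades. SAP 3.5.3 refers back to 3.5.1 and 3.5.2, and the withdrawal-specific rule in 3.5.1 most plausibly governs.

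**Conclusion.** The point holds in limited form. The Week 24 denominator is unstated. On the likely observed-case reading, the primary rate omits known failures and neither the PP analysis nor the interim analysis is set up to show it. The exemption in SAP 3.3 is wrong as written: it has no effect on the Week 24 PP rate, it conflicts with the completion condition in its own section and in Protocol 7.2, and SAP 1.3 does not record the departure.

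One or two failures per site would move the rate by 1.8 to 3.5 points, well inside the planned half-width of 8.3 points. The per-site bound, with all five dropouts as failures, is a fall of 8.2 points, about equal to that half-width. The same fall pooled exceeds the pooled half-width of 5.9 points. These figures rest on 90% observed response, 10 dropouts of 110, and a failure share that the documents do not give. The 81.8% figure is a bound, not a forecast, and 90.9% is the bound on the other side. No test or success threshold exists (Protocol 5.2, SAP 3.4.3.1), so type I error and power are not at issue.

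**What to change.** 1. In SAP 3.4.3.2, state the Week 24 denominator. At both interim and final, report the observed-case rate and the all-ITT rate with missing counted as non-response, per manufacturing site and overall.
2. In SAP 3.3, either count the exempted subjects as Week 24 non-responders in PP and show the same rule in ITT, or delete the exemption. If the rule is kept, say how it treats adverse events classed as possibly related only because relatedness could not be assessed. Protocol 14.4.2 puts those in the possible category, so the rule would otherwise score events of unknown cause as device failures.
3. In SAP 1.3, record the resulting departures from Protocol 7.2 and 7.3.

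Optional: a sensitivity row at interim and final counting subjects with non-protocol correction of the treated folds before Week 24 as non-responders (the Week 2 touch-up with the study device does not count), and one sentence confirming that SAP 3.5.1 governs withdrawal grades.

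The cost is SAP wording and a few table rows, with no new visits or assessments. Reasons for discontinuation are already listed, and aesthetic procedures in the treated area are already asked about (Protocol 6.4.12). The reported rate may be slightly lower. Counting missing as non-response is conservative, because some dropouts, for example COVID-related ones, may be responders. Recorded reasons may be incomplete, since Protocol 6.3.6 does not oblige subjects to give one; the missing-as-non-response row bounds that gap.

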3.5.2 Window for time points

A strict adherence to the visit windows will be required.

Assessments performed out of the planned visit window will be assigned to visit as described in 3.5.1. If both preceding and following planned visits are missing for an performance assessment and the distances are equal, the assignment is performed to the preceding one.

Outcomes not assigned to a planned visit will not be included in the statistical evaluation and will be listed only.

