3.5.3 Unscheduled visits

If applicable, the reason for unscheduled visit assessments will be given in data listings together with the outcome of the unscheduled assessment.

For the statistical analysis the unscheduled assessments will be assigned to a planned visit as scheduled in section 2.3, applying the procedure given in 3.5.1 and 3.5.2.

Individual assessments that were performed between visits, even if the visit was performed for the other assessments will be assigned for analysis to the closest missing visit. If both preceding and following performed visits are missing the assessment and the distances are equal, the assignment is performed to the preceding one.

In case a planned on-site visit cannot take place due to COVID-19 and the investigator performs an unscheduled visit as delayed on-site visit, including all missed assessments foreseen for the cancelled on-site visit, the results of the delayed on-site visit will be assigned for statistical analysis to the on-site visit that had to be cancelled.

In case an unscheduled safety phone call replaces an on-site visit the investigator will also record the subject's GAIS assessment and the subject's satisfaction questionnaire via phone and these results will be assigned for statistical analysis to the on-site visit that had to be cancelled.

Page 20 of 21

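### SAP 3.5.2 assigns out-of-window grades by a rule written for withdrawals, and no section limits how far from Week 24 a grade may lie and still count

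*SAP*

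**What the plan says.** The primary endpoint is the Week 24 response rate on the investigator's live NLF-SRS grading (SAP 3.4.3.2), with a visit window of ± 7 days (SAP 2.3). The rules for grades taken off schedule are spread over three sections:

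- **SAP 3.5.1, withdrawals.** No imputation is allowed. For subjects who leave, "Attempts should be made to perform an early termination visit, which should consist of the assessments planned for the Week 104 visit", and the SAP's list of these includes NLF-SRS. The grade is then placed backward: "Performance assessments at withdrawal will be assigned for analysis to the closest missing visit before withdrawal". The sentence is limited to withdrawals that fall between scheduled visits.
- **SAP 3.5.2, out of window.** "Assessments performed out of the planned visit window will be assigned to visit as described in 3.5.1". A tie-break follows: "If both preceding and following planned visits are missing for an performance assessment and the distances are equal", the earlier visit is used. What cannot be placed is left out: "Outcomes not assigned to a planned visit will not be included in the statistical evaluation and will be listed only".
- **SAP 3.5.3, unscheduled.** These assessments are placed by "applying the procedure given in 3.5.1 and 3.5.2". Individual assessments made between visits, "even if the visit was performed for the other assessments will be assigned for analysis to the closest missing visit". For an on-site visit delayed by COVID-19, "the results of the delayed on-site visit will be assigned for statistical analysis to the on-site visit that had to be cancelled".

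None of the three sections gives a maximum distance or delay. The interim analysis (SAP 4) follows completion of Week 24 by all subjects, and its listing cut-off depends on which assessments are assigned to Week 24 under 3.5.3.

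**The concern.** A rule that looks only backward can never produce a tie between a preceding and a following visit. The tie-break in 3.5.2 therefore presumes a nearest-visit rule that 3.5.1, the section it cites, does not contain. Because unplaced outcomes are only listed, the choice of rule decides whether a subject enters the numerator and denominator of the primary rate. Two programmers working from the same text could derive different Week 24 values.

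Where the assignment is clear, it has no limit. A grade taken long after Week 24 can carry the Week 24 label. The protocol puts the device lifetime at up to 9 months (2.1) and the effect at 6 to 12 months (4.1), so late grades would tend to lower the Week 24 rate. A withdrawal after the interim could also supply a Week 24 value that was missing at the interim, so the interim and final reports could give different primary rates.

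Off-schedule visits are foreseeable. Protocol 10 expects more deviations during the pandemic, including missed and delayed visits, and Protocol 4.6 has sites postpone visits when attendance is not possible.

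**Working it through.** **1. The plan's own interval.** Inputs from SAP 2.2: response rate p = 0.9, n = 50 per manufacturing site, two-sided 95%, normal approximation.

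Half-width = 1.96 × √(p(1 − p)/n) = 1.96 × √(0.09/50) = 0.083, giving [0.817; 0.983], as stated. For about 100 subjects overall: 1.96 × √(0.09/100) = 0.059. The benchmarks are 8.3 points per manufacturing site and 5.9 points overall.

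**2. Target days** (week × 7): Week 4 = 28, Week 24 = 168, Week 36 = 252. The Week 24 window is 168 ± 7 = days 161 to 175.

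**3. The two rules applied to the same grade, with no in-window Week 24 grade:**

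| Grade on | Week 4 | Literal 3.5.2 (backward rule of 3.5.1) | Closest missing visit (3.5.3) |
|---|---|---|---|
| Day 160 | done | no earlier missing visit: listed only | Week 24 (168 − 160 = 8 days) |
| Day 160 | missed | Week 4 (160 − 28 = 132 days) | Week 24 (8 days) |
| Day 176 | either | Week 24 (176 − 168 = 8 days) | Week 24 (8 days) |

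The rules agree for a slightly late grade and disagree for a slightly early one.

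**4. Distance.** With Week 24 missed, a withdrawal grade at Week 34 is taken on day 34 × 7 = 238. The backward rule assigns it to Week 24. It lies 238 − 168 = 70 days after Week 24 and 252 − 238 = 14 days before Week 36. The two visits are 252 − 168 = 84 days apart, so limits below 84/2 = 42 days on each side cannot overlap.

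**5. Effect of one grade on the rate:**

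| Change | Overall, from 90/100 | One manufacturing site, from 45/50 |
|---|---|---|
| Late non-responder added | 90/101 = 89.1% (−0.9) | 45/51 = 88.2% (−1.8) |
| Late responder added | 91/101 = 90.1% (+0.1) | 46/51 = 90.2% (+0.2) |
| Early responder listed only | 89/99 = 89.9% (−0.1) | 44/49 = 89.8% (−0.2) |
| Early non-responder listed only | 90/99 = 90.9% (+0.9) | 45/49 = 91.8% (+1.8) |

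**6. Range under assumptions.** The documents do not give the number affected. Assume 1 to 5 subjects overall and 1 to 3 in one site, with 10 to 30% of them graded differently than they would have been at Week 24. Changing the grade of a subject already counted moves the rate by 1 point in 100 or 2 points in 50. The shift is then 0.1 × 1 × 1 = 0.1 to 0.3 × 5 × 1 = 1.5 points overall, and 0.1 × 1 × 2 = 0.2 to 0.3 × 3 × 2 = 1.8 points in one site. If all the assumed late grades were added as non-responders, the rates would be 90/105 = 85.7% (−4.3) and 45/53 = 84.9% (−5.1), still inside the half-widths.

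**The case against.** The strongest reply is that the intent can be recovered: backward for withdrawals, closest missing visit for everything else. The tie-breaks in 3.5.2 and 3.5.3 are nearly identical, and the clause in 3.5.3 on individual assessments can be read to cover a whole visit made out of window. On that reading day 160 goes to Week 24. This is fair and probably what was meant, but 3.5.2 still names the wrong section.

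The early grade is also the rarer case. The protocol foresees missed, postponed and delayed visits, not early ones, and calls for NLF-SRS off schedule mainly at COVID replacement visits and early termination, each of which has its own rule. That limits the likely number. It does not correct the text.

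Safeguards exist: sites must keep to the windows (SAP 3.5.2), Visit 6 is not among the examples of discretionary visits (Protocol 4.6), deviations are reviewed before hard lock (Protocol 10), and the per-protocol set requires Week 24 completed without major deviations (SAP 3.3). They are partial, because the per-protocol set serves the final analysis only and the interim performance analysis is intent-to-treat only (SAP 4).

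Three stronger readings are tempting and not supported:

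- **That Week 24 is undefined for every subject seen off schedule.** Between-visit withdrawal grades and COVID-delayed visits are clearly assigned. They lack only a limit.
- **That a Week 50 withdrawal grade jumps back over a completed Week 36 to Week 24 (350 − 168 = 182 days).** The words of 3.5.1 allow it. But that rule concerns withdrawals between scheduled visits, and the neighbouring sections speak of the preceding and following visits, so it is arguable that only adjacent visits are meant. The point does not need this case.
- **That the rate could swing by about 9 points, 45/55 = 81.8% against 50/55 = 90.9%.** This treats about 5 planned dropouts per site as all supplying Week 24 grades. The dropouts are the allowance for reaching 100 subjects at Week 24 (Protocol 6.3.1), and a subject who leaves before Week 24 cannot fill that visit under the backward rule.

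**Conclusion.** The point holds in two limited parts, both confined to subjects without an in-window Week 24 grade. The cross-reference in 3.5.2 is wrong: read literally, it drops or mislabels an early Week 24 grade while keeping an equally late one. Separately, withdrawal and COVID-delayed grades may be used as Week 24 values at any distance, and a withdrawal grade may arrive after the interim.

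Severity is minor to moderate. One late non-responder costs 0.9 point overall or 1.8 points in one manufacturing site, against half-widths of 5.9 and 8.3. The likely total is small, but it rests on assumed numbers of affected subjects and assumed differences in grading. There is no hypothesis test (SAP 3.4.3.1), so the harm is confined to the estimate, its interval and the agreement between the interim and final reports. The expected direction for late grades, downward, is an inference from the protocol's statements on duration of effect.

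**What to change.** - In SAP 3.5.2, replace the reference to 3.5.1 with the closest-missing-visit rule of 3.5.3, ties going to the preceding visit. State in 3.5.1 that the backward rule applies to withdrawal grades only.
- Before the interim, set a maximum distance, justified by the sponsor, beyond which a withdrawal, unscheduled or delayed grade is listed and not used as the Week 24 value. Any limit below 42 days avoids overlap with Week 36; the exact figure is a judgement for the sponsor. The limit must cover unscheduled grades too: under the closest-missing-visit rule, a Week 6 grade with Week 4 done and nothing later would become Week 24, (24 − 6) × 7 = 126 days early.
- Add a sensitivity analysis of the primary endpoint restricted to grades at Week 24 ± 7 days, at both interim and final.
- Report the number of off-window Week 24 values by manufacturing site, and any Week 24 value that changed after the interim.

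The cost is SAP wording and one sensitivity table; no new data are needed. The downside is that a few more Week 24 values, including visits long delayed by COVID-19, may be classed as missing in the main analysis, where nothing is imputed.
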